5.1.2 Hypotheses and Statistical Methods for Secondary Objectives

5.1.2.1 Hypotheses

All analyses will be descriptive; no hypothesis will be tested.

5.1.2.2 Statistical Methods

Safety

The point estimates and their 95% CI of the following parameter will be presented 7 days after each vaccination (D7 for Cohorts 1, 2, 3 and 4, and D63 for Cohorts 2 and 4) for each vaccine group by baseline serostatus:

- Proportion of participants with detectable/quantified virus shedding
- Arithmetic mean of vaccine virus shedding measured by [REDACTED]

Infectivity

The point estimate and its 95% CI of the following parameters will be presented after vaccination 1 (D56) for Cohorts 1, 2, 3 and 4, and after vaccination 2 (D84) for Cohorts 2 and 4 for each vaccine group by baseline serostatus:

- Proportion of vaccinees infected with the vaccine virus. Infection defined as detection of vaccine virus strain in nasal swab by [REDACTED] and / or a \geq 4-fold rise in RSV A serum neutralizing antibody titers or RSV serum anti-F IgG antibody titers.

Immunogenicity

The point estimates of GMT and GMTR and their 95% CI will be presented by vaccine group for the following endpoints:

- RSV A serum neutralizing antibody titers by D56 for Cohorts 1, 2, 3 and 4, and by D84 for Cohorts 2 and 4, in RSV-experienced participants
- RSV serum anti-F IgG antibody titers by D56 for Cohorts 1, 2, 3 and 4, and by D84 for Cohorts 2 and 4 by baseline serostatus.
- RSV A serum neutralizing and anti-RSV F IgG antibody titers after RSV season or at least 5 months after last vaccine administration by baseline serostatus.

Seroresponse using various thresholds regarding fold-rise or post-vaccination titer value may also be presented, as applicable.

Main immunogenicity analyses will be presented by baseline serostatus and age group (< 12 months *versus* \geq 12 months).

5.1.3 Statistical Methods for Exploratory Objectives

Safety

Solicited ARs, unsolicited AEs (including SAEs), MAAEs and AESIs will be summarized. Analyses described in Section 5.1.1.2 will be presented by vaccine group after each and any vaccination by baseline serostatus.

Immunogenicity

Similar analyses as described as for secondary immunogenicity objectives will be performed on exploratory immunogenicity endpoints.

Analyses on RSV A and RSV B serum anti-Gcc IgG antibody responses planned in the protocol will finally not be produced for this study, please refer to section 5.7 for the rationale.

Efficacy

RSV Medically attended respiratory illness collected during the RSV season will be summarized. The main parameters will be described with 95% CI. At least the following parameters will be presented by vaccine group:

- RSV medically attended acute respiratory illness (RSV MAARI) by SOC and PT, intensity, time of onset, and duration
- RSV medically attended lower respiratory tract illness (RSV MAALRI) by SOC and PT, intensity, time of onset, and duration
- Vaccine Efficacy (VE)

The VE of RSVt vaccine (low dose or high dose, as applicable) will be estimated for each endpoint as follows:

$$VE = 1 - \frac{C_{RSV}/N_{RSV}}{C_P/N_P}$$

where:

- C_{RSV} and C_P are the numbers of RSV MAARI / RSV MAALRI cases meeting the considered definition in the RSV (low dose or high dose) and Placebo groups, respectively.
- N_{RSV} and N_P are the numbers of participants in the RSV (low dose or high dose) and Placebo groups, respectively.

The CI will be calculated using the exact method conditional on the total number of cases in both groups described by Breslow & Day (2).

Let $q = \frac{C_{RSV}}{C_{RSV}+C_P}$, the proportion of cases belonging to RSV group (low dose or high dose) among the total number of cases in the considered RSV vaccine group and Placebo group. Given the total number of cases, C_{RSV} has a binomial distribution ($C_{RSV}+C_P$, q). Thus, a CI for q may be constructed using the exact Clopper-Pearson method for binomial proportions (1).

As $\frac{q}{1-q} = \frac{C_{RSV}}{C_P}$, the VE estimate given above may be restated as follows:

$$VE = 1 - \frac{C_{RSV}/N_{RSV}}{C_P/N_P} = 1 - \frac{N_P}{N_{RSV}} \times \frac{q}{1-q}, \text{ which is a strictly decreasing function of } q.$$

Finally, for each efficacy endpoint, a CI of the VE will be constructed based on the CI of q .

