1:1 randomized, placebo-controlled, 1 dose of RSV Δ NS2/ Δ 1313/I1314L [REDACTED], 2 administrations ([REDACTED] in total per administration) at D0 and D56, n=20 per vaccine group. Participant enrollment will be initiated at approximately 4 sites in Latin America ((Argentina and Chile) at the earliest in November/December 2020. The first and the second vaccine administrations (D0 and D56, respectively) will be completed at least 5 days before the beginning

of the RSV season (the average 5-month RSV season in the southern hemisphere is 01 May to 30 September).

Cohort 3 (Northern Hemisphere):

1:1 randomized, placebo-controlled, 1 dose of RSV ΔNS2/Δ1313/I1314L [REDACTED] [REDACTED]
1 administration ([REDACTED] per administration in total) at D0, n=20 per vaccine group. Participant enrollment will be initiated at approximately 30 sites in the US in April 2021. Vaccine administrations will be completed before 31 May 2021. If recruitment in Cohort 3 does not reach the goal of n=40, no attempt will be made to include more participants receiving 1 administration in Cohort 4.

Cohort 4 (Northern and Southern Hemisphere):

1:1:1 randomized, placebo-controlled, 2 doses of RSV ΔNS2/Δ1313/I1314L ([REDACTED]
[REDACTED]), 2 administrations ([REDACTED] per administration in total) at D0 and D56, n=60 per vaccine group. Participant enrollment will be initiated at approximately 30 sites in the US at the earliest in June 2021, approximately 2 sites in Canada at the earliest in May 2022, approximately 2 sites in Chile at the earliest in November 2021, approximately 2 sites in Honduras at the earliest in April 2022, and approximately 2 sites in South Africa at the earliest in June 2022.

The first and the second vaccine administrations will be completed at any time of the year, including the winter RSV season, regardless if normal RSV seasonality is restored after the disruption due to COVID-19 non-pharmaceutical interventions.

Blood Sampling:

All participants screened for inclusion in Cohorts 1, 2, 3 and 4 will provide a blood sample at enrollment (Visit 01), for baseline RSV serum antibody testing.

All participants in each vaccine group in Cohorts 1, 2, 3 and 4 will provide a blood sample at the D56 Visit (before vaccination 2 for Cohorts 2 and 4), for the measurement of post-vaccination serum antibody titers to RSV.

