Based on previous data regarding the seasonality of RSV in the US, Canada, Chile, Honduras, and South Africa, surveillance for RSV-associated disease will be largely conducted during the NH (1st November to 31st March) and SH (1st May to 30 September) RSV seasons respectively, adjusted for local site RSV seasonality. Due to the disruption of the seasonal pattern of RSV globally (24) (25), it is unclear when the normal seasonal transmission will resume though there is some suggestion of a rebound in the winter of 2021–2022 in the NH (26). Because of the unpredictability of the RSV season due to the impact of COVID-19 nonpharmaceutical interventions, study participant enrollment and vaccination will continue regardless of RSV activity. Study participants enrolled before the routine winter RSV season for that locality will be followed up until the consequent month after the end of the routine season (i.e. April for NH and October for SH). Study participants enrolled during the routine RSV season (i.e. November to March for NH and May to September for SH) will be followed up for at least 5 months after the last vaccine administration. During the RSV season or post-vaccination RSV surveillance, study participants will be monitored for symptomatic medically attended respiratory illness. Note, this surveillance may overlap with the Acute and Post-Acute phases. In this case, evaluations required for each of the relevant phases of the study will be conducted.

Evaluation of two vaccine doses [REDACTED]:

Previous Phase Ia studies done by the NIH have demonstrated that the [REDACTED] dose of RSV ΔNS2/Δ1313/I1314L vaccine resulted in better infectivity and neutralizing antibody seroresponse than the [REDACTED] dose, with no evidence of an excess of respiratory tract illness associated with receipt of the higher dose ([REDACTED]). However, in these studies, the vaccine was administered intranasally using a sterile, needle-less 1 mL oral syringe, at a volume of 0.5 mL as nasal drops (approximately 0.25 mL per nostril). In VAD00001 study, the vaccine would be administered at a total volume of [REDACTED] [REDACTED] [REDACTED]

Use of an intranasal [REDACTED]
may improve the overall delivery of the vaccine and may increase replication in both doses. Use
of the [REDACTED] may also improve the infectivity of the low dose [REDACTED]
doses will be the minimal doses explored using the [REDACTED]

Evaluation of two administrations of vaccine doses:

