9.3.4 Efficacy

9.3.4.1 Efficacy Endpoints

The exploratory endpoints for the evaluation of efficacy assessed through the RSV season or post-vaccination surveillance period are:

- RSV medically attended acute respiratory illness (RSV MAARI)
- RSV medically attended acute lower respiratory illness (RSV MAALRI)
- A diagnosis of RSV MAARI requires a respiratory sample positive for RSV by [REDACTED] AND documented physical exam findings of respiratory tract illness including any of the following:
 - Fever
 - Acute otitis media
 - Upper respiratory tract illness:
 - Runny nose/rhinorrhea
 - Pharyngitis
 - Cough without LRI
 - Lower respiratory tract illness (see MAALRI below)
- A diagnosis of RSV MAALRI (a subset of MAARI) requires a respiratory sample positive for RSV by [REDACTED] AND documented physical exam findings of lower respiratory tract illness including any of the following:
 - Stridor
 - Rales
 - Tachypnea
 - Acute wheeze
 - Pneumonia
 - Laryngotracheobronchitis

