12.1.3 Statistical Methods for Exploratory Objectives

Safety

Solicited ARs, unsolicited AEs (including SAEs), MAAEs and AESIs will be summarized. The main parameters will be described with 95% CI. Main parameters, as described in [Section 12.1.1.2](#), will be presented by vaccine group after each and any vaccination by baseline serostatus.

Immunogenicity

The point estimates of GMT and GMTR and their 95% CI will be presented by vaccine group and by baseline serostatus for the following endpoints:

- RSV A serum neutralizing antibody titers by D56 for Cohorts 1, 2, 3 and 4, and by D84 for Cohorts 2 and 4, converted into international units (IU)/mL.
- RSV A serum neutralizing antibody titers converted into IU/mL, after the RSV season or at least 5 months after last vaccine administration.
- RSV B serum neutralizing antibody titers by D56 for Cohorts 1, 2, 3 and 4, and by D84 for Cohorts 2 and 4.
- RSV B serum neutralizing antibody titers by D56 for Cohorts 1, 2, 3 and 4, and by D84 for Cohorts 2 and 4, converted into IU/mL.
- RSV B serum neutralizing antibody titers after the RSV season or at least 5 months after last vaccine administration.
- RSV B serum neutralizing antibody titers converted into IU/mL, after the RSV season or at least 5 months after last vaccine administration.
- RSV A and RSV B serum anti-Gcc IgG antibody titers by D56 for Cohorts 1, 2, 3 and 4, and by D84 for Cohorts 2 and 4.

- RSV A and RSV B serum anti-Gcc IgG antibody titers after the RSV season or at least 5 months after last vaccine administration.
- RSV serum anti-F IgA antibody titers by D56 for Cohorts 1, 2, 3 and 4, and by D84 for Cohorts 2 and 4.
- RSV serum anti-F IgA antibody titers after the RSV season or at least 5 months after last vaccine administration.

Seroresponse may also be presented, as applicable.

Efficacy

RSV Medically attended respiratory illness collected during the RSV season or at least 5 months after last vaccine administration will be summarized. The main parameters will be described with 95% CI. At least the following parameters will be presented by vaccine group:

- RSV medically attended acute respiratory illness (RSV MAARI) by SOC and PT, intensity, time to onset, and duration
- RSV medically attended lower respiratory illness (RSV MAALRI) by SOC and PT, intensity, time to onset, and duration

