Exploratory Efficacy Objective

- To describe the frequency and severity of RSV-associated, medically attended acute respiratory illness (RSV MAARI) and RSV-associated, medically attended, acute lower respiratory illness (RSV MAALRI) in all infants and toddlers in each vaccine group during the RSV season or at least 5 months after last vaccine administration.

3 Description of the Overall Trial Design and Plan

[figure not shown]

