4.3.4 Efficacy

See Section 9.3.4 of the protocol.

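### The SAP is inconsistent on the exploratory efficacy window: section 5.1.3 names the RSV season only, while its own objective and the protocol also include the 5-month post-vaccination period

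*SAP*

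**What the plan says.** The efficacy part of SAP 5.1.3 opens with "RSV Medically attended respiratory illness collected during the RSV season will be summarized". The MAARI and MAALRI summaries and the VE formula follow under that sentence. VE is one minus the ratio of C_RSV/N_RSV to C_P/N_P, where N is the number of participants in the group.

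Four other places describe a longer window:

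- Protocol 12.1.3, same sentence: "RSV Medically attended respiratory illness collected during the RSV season or at least 5 months after last vaccine administration will be summarized".
- SAP 2.3, exploratory efficacy objective: frequency and severity "in all infants and toddlers in each vaccine group during the RSV season or at least 5 months after last vaccine administration".
- SAP 4.3.4, efficacy endpoints: "See Section 9.3.4 of the protocol". That protocol section (9.3.4.1) lists endpoints "assessed through the RSV season or post-vaccination surveillance period are" the two RSV illness definitions.
- Protocol 5.1.2, on Cohort 4: children enrolled during the routine season "will be followed up for at least 5 months after the last vaccine administration". The notes to SAP Table 3.3 repeat this.

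SAP 5.7 lists one change from the protocol, the dropped anti-Gcc analyses. It does not mention the efficacy window.

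**The concern.** The longer window matters because of how Cohort 4 is run. It holds 180 of the 300 participants, and Protocol 5.1.1 states: "The first and the second vaccine administrations will be completed at any time of the year, including the winter RSV season". Protocol 5.1.2 explains that RSV seasonality was disrupted and unpredictable. A child first vaccinated late in the season receives dose 2 after the season has ended on its average dates. For that child the 5-month period is the planned surveillance, and the season covers little of it.

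If a programmer follows SAP 5.1.3 as written, an RSV illness in that period is not counted, but the child still adds one to N_RSV or N_P. A programmer who follows SAP 2.3 and 4.3.4 counts it. Both could claim to follow the SAP, yet they could report different case counts and different VE estimates.

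**Working it through.** **The plan's own figure.** The documents give no number for the efficacy window, so there is nothing to reproduce on this point.

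**Inputs.** The northern-hemisphere (NH) season is 01 November to 31 March (Protocol 5.1.4.2), which is 151 days outside a leap year. Dose 2 is at D56 (SAP 3.1). Follow-up is at least 5 months after the last dose (Protocol 5.1.2), taken here as 152 days, so 56 + 152 = 208 days from D0. Assumptions: enrolment is even over the season, the average season dates apply, and follow-up stops at the 5-month minimum.

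**Formulas.** Let s = 0, …, 150 be the days from 01 November to enrolment.

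- In-season days from D0 = 151 − s. The mean is (151 + 1)/2 = 76. 76/208 = 36.5%, so 63.5% is excluded.
- In-season days after dose 2 = max(0, 151 − 56 − s) = max(0, 95 − s). The sum over s is 95 × 96/2 = 4,560, and the mean is 4,560/151 = 30.2. 30.2/152 = 19.9%, so 80.1% is excluded.
- Enrolment dates with no in-season day after dose 2 are s = 95 to 150: 56 of 151 = 37%.

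**By enrolment date (NH).**

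| Enrolled | In season, from D0 | Excluded | In season, after dose 2 | Excluded |
|---|---|---|---|---|
| 01 Nov | 151 of 208 | 27% | 95 of 152 | 37.5% |
| 01 Dec | 121 of 208 | 42% | 65 of 152 | 57% |
| 01 Feb | 59 of 208 | 72% | 3 of 152 | 98% |
| 01 Mar | 31 of 208 | 85% | 0 of 152 | 100% |

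A count by calendar months gives the same averages: 63% from D0 and 80% after dose 2, in both hemispheres. By that count, more than half of post-dose-2 time is excluded for NH enrolment from 21 November on. For time from D0 this starts at 20 December.

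**Effect on VE.** Case counts are not given, so these are assumed, with 60 per group as in Cohort 4. The SAP's method takes the Clopper-Pearson interval for q = C_RSV/(C_RSV + C_P) and converts it by VE = 1 − (N_P/N_RSV) × q/(1 − q).

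- 6 versus 12 cases: VE = 1 − (6/60)/(12/60) = 50%, 95% CI −44% to 85%.
- 3 versus 6 cases (half lost in each group): VE = 50%, 95% CI −134% to 92%.

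The estimate does not move, and the interval widens.

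**What is collected.** Protocol 5.1.4.2 has illness visits scheduled for medically attended fever, URI, LRI or otitis media during both the season and the post-vaccination surveillance. Table 5-4 lists only SAEs in its row for the post-season period or at least 5 months after the last administration. The two do not agree on what out-of-season illness data will exist.

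**The case against.** The strongest reply is that the SAP as a whole does not adopt a season-only analysis. Its objective keeps the longer window, its endpoints come from Protocol 9.3.4, its case definition in 4.4.3 carries no dates, and the VE numerator is cases meeting that definition. The term RSV season is also used loosely: SAP Table 3.3 places phone contacts 31 to 40 between Visit 05 and Visit 06, yet the note on phone contacts describes them as made during the season. This stands. A reader might infer that the sponsor decided to discard out-of-season cases; the documents do not support that, and a dropped phrase is more likely.

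A reader might also infer that VE would be biased, or would no longer describe the two-administration schedule. That does not follow either. Any common window, with all participants in the group as N, gives a valid attack-rate ratio. Randomised groups lose follow-up time alike, so keeping N as a head count is not itself an error. The point estimate shifts only if efficacy varies over time or by number of doses.

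The percentages also need care. Protocol 5.1.2 adjusts surveillance for local seasonality, so the dates are not fixed. The figures cover only children enrolled in season, whose number is not stated. Children enrolled before the season are followed through it.

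What the reply does not remove is that the operative analysis sentence differs from the protocol, from SAP 2.3 and from SAP 4.3.4, with no declared change.

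**Conclusion.** The inconsistency is real and should be corrected. On a literal reading of SAP 5.1.3, about 63% of follow-up from D0 and 80% of post-dose-2 follow-up would be excluded on average for Cohort 4 children enrolled in season. This rests on the assumptions listed above. On the 01 November enrolment date the figures are only 27% and 37.5%. The overall share of VE cases affected cannot be derived.

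The sure consequence is fewer cases, a wider VE interval, and a result that depends on which SAP section is followed. The priority is minor: the endpoint is exploratory, all analyses are descriptive, and Protocol 5.1.2 bases dose selection on safety, infectivity and immunogenicity, not on VE.

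**What to change.** 1. In SAP 5.1.3, restore the protocol's alternative of at least 5 months after the last vaccine administration.
2. State one case-counting window, from a named start to the post-season or 5-month visit (Visit 04 for Cohorts 1 and 3, Visit 06 for Cohorts 2 and 4). The end must be named because a period of at least 5 months has no upper limit. Use this window for the MAARI and MAALRI summaries, C_RSV and C_P, and keep N as all participants in the group.
3. If season-only counting is intended, say so in SAP 5.7 with the reason, and align SAP 2.3 and 4.3.4.
4. Reconcile Protocol 5.1.4.2 with Table 5-4, so that the illness data collected match the window analysed.

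The first three items are a few sentences in the SAP. The fourth is a clarification of the protocol. Until it is settled, it should not be assumed that all out-of-season illness data are available.

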5.2 Analysis Sets

The following analysis sets will be used: The Full Analysis Set, the Per-Protocol Analysis Set, and the Safety Analysis Set.

5.2.1 Full Analysis Set

The full analysis set (FAS) is defined as the subset of randomized participants who received at least 1 administration of the study vaccine.

5.2.2 Safety Analysis Set

The safety analysis set (SafAS) is defined as those participants who have received at least 1 administration of the study vaccine.

All participants will have their safety analyzed after each administration according to the vaccine they actually received and after any vaccination according to the vaccine received at the first administration.

Safety data recorded for a vaccine received out of the protocol design will be excluded from the analysis (and listed separately).

5.2.3 Per-Protocol Analysis Set

The per-protocol analysis set (PPAS) is a subset of the FAS. Two specific PPAS will be defined: PPAS1 after 1 administration (for participants in Cohorts 1, 2, 3 and 4) and PPAS2 after 2 administrations (for participants in Cohorts 2 and 4).

The participants presenting with at least one of the following relevant protocol deviations will be excluded from the PPAS:

- Baseline serology blood sample was not collected at visit 01 (D0).
- Participant with temporary contraindication did not receive vaccination 1 in the proper time window from randomization [*i.e., within 5 days of randomization*]
- Participant did not meet all protocol-specified inclusion criteria or met at least one of the protocol-specified exclusion criteria
- Participant did not receive vaccine / did not complete the vaccination schedule
- Participant received a vaccine other than the one that he / she was randomized
- Preparation and / or administration of vaccine not done as per-protocol
- Participant received a protocol-prohibited therapy before the post-vaccination serology blood sample (see Section 6.7.1 of the protocol)
- Participant with confirmed diagnosis of wild-type (wt) RSV before the post-vaccination serology blood sample
- Participant with an emergency unblinding performed by the Investigator

The participants presenting with at least one of the following relevant protocol deviations will be excluded from the PPAS1 only:

- Post-vaccination 1 serology blood sample not collected at visit 03
- Post-vaccination 1 serology blood sample not collected at visit 03 in the proper time window [*i.e., date of vaccination 1 + 56 days; date of vaccination 1 + 66 days*]*

The participants presenting with at least one of the following relevant protocol deviations will be excluded from the PPAS2 only (for participants in Cohorts 2 and 4):

- Participant did not receive vaccination 2 at visit 03 in the proper time window [*i.e., date of vaccination 1 + 56 days; date of vaccination 1 + 66 days*]*
- Post-vaccination 2 serology blood sample not collected at visit 05
- Post-vaccination 2 serology blood sample not collected at visit 05 in the proper time window [*i.e., date of vaccination 2 + 28 days; date of vaccination 2 + 38 days*]*

In addition to the reasons listed above, participants will also be excluded from the PPAS if their baseline serology sample or their post-vaccination serology sample did not produce a valid test result (*i.e., result for RSV A serum neutralizing antibody titers is missing*).

Note: For PPAS1 (after 1 administration), timepoints to be considered are: D0 for vaccination and D56 (visit 03) for the post-vaccination serology sample. For PPAS2 (after 2 administrations), timepoints to be considered are: both D0 (visit 01) and D56 (visit 03) for vaccinations and D84 (visit 05) for the post-vaccination serology sample.

The definition may be complemented with additional criteria for exclusion after the review of protocol deviations reported on site. During the review, such deviations will be marked with exclusion from analysis set for programming purpose.

*Time windows have been extended in the PPAS definition compared to study protocol for clinical relevance.

